5.2.5.3 Primary Analysis of Secondary Endpoint: PFS

The analysis of PFS is based on the ITT analysis set. The number and percentage of patients experiencing a PFS event (broken down by type of event/censoring) and Kaplan-Meier plots of PFS will be presented. The median PFS and its two-sided 95% CI will be estimated using the Kaplan-Meier method (if patient numbers allow).

The treatment status at progression of patients at the time of analysis will be summarised. This includes the number (%) of patients who were on treatment at the time of progression, the number (%) of patients who discontinued study treatment prior to progression, the number (%) of patients who have not progressed and were on treatment or discontinued treatment.

A summary of the ‘potential’ duration of follow-up for PFS is included using median (range). This is presented for censored patients (including all types of PFS censoring).

The proportion of patients alive and progression free at every 3 months (3, 6, 9, 12, etc.) and associated two-sided 95% CI will be estimated using the Kaplan-Meier method.

5.2.5.4 Sensitivity Analysis of PFS Endpoint

A sensitivity analysis will be performed censoring PFS at the date of the last progression-free disease assessment prior to initiation of subsequent anticancer treatment.

Separately, a sensitivity analysis will also be conducted to assess the impact of COVID-19 related deaths on PFS. That is, patients who had a PFS event due to death where the primary or secondary cause of death was COVID-19 infection or COVID-19 infection was reported as a fatal AE, will be censored on the last available tumour assessment prior to COVID-19 infection related death.

5.2.6 Secondary Endpoint: Overall Survival

The Overall Survival (OS) is a secondary efficacy endpoint.

Part B.

If data permits, this endpoint will also be considered for Part A as exploratory.

5.2.6.1 Definition

Overall survival is defined as the time from the date of first dose until death due to any cause regardless of whether the patient withdraws from study therapy or receives another anticancer therapy.

5.2.6.2 Derivations

OS (months) = (date of death or censoring – date of first dose + 1) / (365.25/12).

Any patient not known to have died at the time of analysis will be censored based on the last recorded date on which the patient was known to be alive. Patients known to be alive or dead after the data cut-off for analysis will be censored at the DCO. Patients lost to follow-up will be censored at the date the patient is last known to have been alive.

Note: Survival calls will be made in the week following the date of DCO for the analysis, and if patients are confirmed to be alive or if the death date is post the DCO date these patients will be censored at the date of DCO. The status of ongoing, withdrawn (from the study) and “lost to follow-up” patients at the time of the final OS analysis should be obtained by the site personnel by checking the patient’s notes, hospital records, contacting the patient’s general practitioner and checking publicly-available death registries. In the event that the patient has actively withdrawn consent to the processing of their personal data, the vital status of the patient can be obtained by site personnel from publicly available resources where it is possible to do so under applicable local laws.

Note: For any OS analysis performed prior to the final OS analysis, in the absence of survival calls being made, it may be necessary to use all relevant CRF fields to determine the last recorded date on which the patient was known to be alive for those patients still on treatment (since the SURVIVE module is only completed for patients off treatment if a survival sweep is not performed). The last date for each individual patient is defined as the latest among the following dates recorded on the CRFs:

- AE start, stop and change in severity dates
- Admission and discharge dates of hospitalization
- Study treatment date
- End of treatment date
- Concomitant medication start and stop dates
- Laboratory test dates
- Date of vital signs
- Disease assessment dates on CRF
- Start and stop dates of alternative anticancer treatment
- Date last known alive on survival status CRF
- End of study date

Duration of follow-up for OS is defined as follows:

Duration of follow-up for OS (months) = (date of death or censoring (date last known to be alive) – date of first dose + 1) / (365.25/12).

5.2.6.3 Handling of Dropouts and Missing Data

If a patient is known to have died where only a partial death date is available, then the date of death is imputed as the latest of the last date known to be alive +1 from the database and the death date using the available information provided:

- For Missing day only – using the 1st of the month.
- For Missing day and Month – using the 1st of January.

If there is evidence of death but the date is entirely missing, it is treated as missing, i.e., censored at the last known alive date.

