7.3 Lost to Follow-up

A patient will be considered lost to follow-up if he/she repeatedly fails to return for scheduled visits and is unable to be contacted by the study site.

The following actions must be taken if a patient fails to return to the clinic for a required study visit:

- The site must attempt to contact the patient and reschedule the missed visit as soon as possible and counsel the patient on the importance of maintaining the assigned visit schedule and ascertain whether or not the patient wishes to and/or should continue in the study.
- Before a patient is deemed lost to follow-up, the Investigator or designee must make every effort to regain contact with the patient (where possible, 3 telephone calls and, if necessary, a certified letter to the patient's last known mailing address or local equivalent methods). These contact attempts should be documented in the patient's medical record.

- Should the patient continue to be unreachable, he/she will be considered to have withdrawn from the study.
- Site personnel, or an independent third party, will attempt to collect the vital status of the patient within legal and ethical boundaries for all patients enrolled in the study, including those who did not get study intervention. Public sources may be searched for vital status information. If vital status is determined as deceased, this will be documented and the patient will not be considered lost to follow-up. Sponsor personnel will not be involved in any attempts to collect vital status information.

Discontinuation of specific sites or of the study as a whole are handled as part of [Appendix A](#).

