Progression-free survival is defined as the time from date of first dose to date of objective disease progression or death (by any cause in the absence of progression) regardless of whether the patient withdraws from treatment or receives another anti-lymphoma therapy prior to progression.

Patients who have not progressed or died at the time of analysis will be censored at the time of the latest date of assessment from their last evaluable assessment. The PFS time will always be derived based on scan/assessment dates and not on visit dates.

Kaplan-Meier plots of PFS will be presented. Summaries of the number and percentage of patients experiencing a PFS event, and the type of event (progression or death) will be provided along with the median PFS, its 95% CI, and the proportion of patients who were progression-free at 6, 12, and 18 months.

The treatment status at progression of patients at the time of analysis will be summarised. This will include the number and percentage of patients who were on treatment at the time of progression, the number and percentage of patients who discontinued study intervention prior to progression, the number and percentage of patients who have not progressed and were on treatment or discontinued treatment. This will also provide a distribution of number of days prior to progression for the patients who have discontinued treatment.

Overall Survival

Overall survival is defined as the time from date of first dose until death due to any cause regardless of whether patient withdraws from treatment or receives another anti-lymphoma therapy. Any patient not known to have died at the time of analysis will be censored on the last recorded date on which the patient was known to be alive.

Note: Survival follow-up phone calls will be made in the week following the date of DCO for the analysis, if patients are confirmed to be alive or if the death date is after the DCO date these patients will be censored at the date of DCO.

Overall survival data will be presented similarly to the presentation described for PFS.

Time to Objective Response

Time to objective response is defined as the time from date of first dose until the date of first documented objective response and will include all patients in the response-evaluable analysis set who had a response.

The TTR will be summarised (ie, number of patients [%] based upon the number of responders) by scheduled assessment timepoint that the response was first observed.

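### For overall survival, the SAP censors a death whose date is entirely missing, contrary to the plan's own definition of an OS event

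*SAP*

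**What the plan says.** SAP 5.2.6.1 defines the endpoint: "Overall survival is defined as the time from the date of first dose until death due to any cause". SAP 5.2.6.2 states who is censored: "Any patient not known to have died at the time of analysis will be censored based on the last recorded date". Protocol 9.4.2 has the same rule: "Any patient not known to have died at the time of analysis will be censored on the last recorded date". In both, the date meant is the patient's last known alive date. Deaths after the data cut-off (DCO) are censored at the DCO.

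SAP 5.2.6.3 then treats incomplete death dates in two ways.

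- **Partial date:** "If a patient is known to have died where only a partial death date is available, then the date of death is imputed", and the death stays an event. The imputed date is the later of last known alive plus one day and the first of the known month (or 1 January if only the year is known).
- **No date:** a death that is evident but wholly undated gets a different rule: "it is treated as missing, i.e., censored at the last known alive date". It is therefore not an OS event.

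SAP 4.3.8 repeats the partial-date rule and has nothing for an entirely missing date. SAP 5.2.6.4 reports both the number of OS events and the number of patients who have died. The only OS sensitivity analysis (SAP 5.2.6.5) concerns COVID-19 deaths. SAP sections 3 and 9 declare no change from the protocol's analyses.

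**The concern.** A patient with established death does not belong to the group that either document says is censored at last known alive. Kaplan-Meier assumes that a censored patient has the same future survival as those still at risk; here the patient is censored precisely because there was none. The error runs in one direction, towards longer survival. It would reach the OS curve, its median and the 3-monthly proportions alive. The OS event count could also be lower than the reported number of deaths, with nothing in the plan to explain the gap.

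The follow-up scheme leaves room for such cases. Survival is checked every 3 months (protocol section 8, Follow-up Period), partly through family or the current physician (protocol 7.1.1) or public sources (protocol 7.3). Protocol 7.3 adds: "If vital status is determined as deceased, this will be documented and the patient will not be considered lost to follow-up". Under SAP 5.2.6.3, a patient found dead in this way but without a date is nevertheless handled exactly like one lost to follow-up.

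**Working it through.** **1. The two rules side by side.** Take a patient last known alive on 10 March (a made-up date).

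- Only the year of death is known, and it is that same year. The later of 1 January and 11 March is 11 March: an **event** on 11 March.
- The year is also missing: **censored** on 10 March.

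The analysis time moves by one day, but the status changes from event to censored. For a given time, changing an event to a censoring can never lower the Kaplan-Meier curve.

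**2. Inputs for the size.** The documents give no OS assumption, no expected share of undated deaths and no legible Part B sample sizes. There is no planned figure to reproduce, and everything below is assumed: exponential OS with median 9 months, follow-up uniform on 6 to 18 months, last contact 0 to 3 months before death (3 months being the protocol's contact interval), and a share *m* of observed deaths undated. The simulation used cohorts of 25, with 3,000 cohorts per setting.

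True 12-month OS = 2^(−12/9) = 39.7%.

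**3. Approximate formula.** With constant hazard λ, the rule drops a share *m* of the events and, on average, 1.5 months of follow-up for each. The estimated hazard is about λ(1 − m)/(1 − 1.5mλ), which is below λ whenever the mean gap (1.5 months) is shorter than mean survival 1/λ. Here λ = ln 2/9 = 0.0770, so 1/λ is about 13 months and the bias is upward. Then 12-month OS is about exp(−12λ × ratio), with 12λ = 0.924.

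| m | ratio | formula | simulated, SAP rule | simulated, counted as event |
|---|---|---|---|---|
| 5% | 0.95/0.9942 = 0.956 | 41.3% | 41.6% | 39.9% |
| 10% | 0.90/0.9885 = 0.911 | 43.1% | 42.9% | 39.4% |
| 20% | 0.80/0.9769 = 0.819 | 46.9% | 46.8% | 39.3% |

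Formula and simulation agree to within simulation error. The last column places the death at last known alive, one day before the date proposed below. With m = 0 there is no bias.

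**4. Medians.** With follow-up of 6 to 24 months and a true median of 12 months, the SAP rule gives about 12.3, 12.6, 13.2 and 14.8 months at m = 2%, 5%, 10% and 20%. Counting the deaths as events at last known alive plus one day gives 11.9 to 12.0 at every m. With a true median of 6 months, the rule gives about 6.1, 6.3, 6.6 and 7.3.

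**5. Number of patients.** With a true median of 12 months, the mean overstatement of 12-month OS, in percentage points, is:

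| Cohort size | 1 undated death | 2 | 3 |
|---|---|---|---|
| 20 | 2.9 | 6.1 | 9.4 |
| 30 | 1.9 | 4.0 | 6.0 |
| 40 | 1.4 | 3.0 | 4.4 |

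Counting them as events instead shifts the estimate by −0.1 to −0.6 points.

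**The case against.** **Frequency.** The documents point to few undated deaths. Date of death is collected for SAEs (protocol 8.3.2), deaths are documented in the eCRF or on a Statement of Death page (8.3.13), death certificates may be used (7.1), and SAP 5.2.6.2 has sites check notes, hospital records, the general practitioner and death registries. Protocol 7.3 requires a death to be documented; it does not say the date will be lacking. This stands: the shares of 5% to 20% are illustrations, not expectations.

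**Precision.** In a cohort of 25, the standard error of 12-month OS is at least √(0.397 × 0.603/25) = 9.8 points. The shifts of 1.9, 3.2 and 7.1 points are about 0.2, 0.3 and 0.7 of that. This also stands, but sampling error does not excuse a bias of known direction that can be removed.

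**Consequence.** No hypothesis test is planned (protocol 9.1), OS is a descriptive secondary endpoint, and the Part B interim looks at response and AEs leading to discontinuation (protocol 10.9.5). No error rate or sample size is affected.

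**Wording.** The SAP speaks of evidence of death for the undated case and of patients known to have died for partial dates. If the evidence does not establish death, ordinary censoring is right. The objection is to censoring deaths that are established.

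**Stronger readings that the text does not support.**

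- A reader might infer that any missing death date leads to censoring. Partial dates are imputed and kept as events.
- A reader might say that these patients are analysed as survivors. They leave the risk set at last known alive, are not carried alive to the DCO, and can still appear in the separate count of deaths.
- A reader might conclude that PFS is overstated too. The rule sits in the OS section only. SAP 5.2.5.2 and Table 2 say nothing about an undated death, and DoR takes its end date from PFS. That is a gap, not a stated error.

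**Conclusion.** The rule is wrong as written, for OS and for entirely missing death dates only. It contradicts the OS definition and the censoring rule in both documents, no sensitivity analysis covers it, and it biases Kaplan-Meier OS upward as long as the gap between last contact and death is short relative to survival. None of the objections removes the contradiction or the direction.

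The size cannot be fixed from the documents. It is zero if every death has at least a year. Under the assumptions above, one undated death in a cohort of 20 to 40 adds about 1.4 to 2.9 points to 12-month OS. It should be corrected because the remedy is short and the cohorts may be small, but it does not threaten the trial's primary conclusions.

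**What to change.** In SAP 5.2.6.3, with the same text in 4.3.8:

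1. Count a known death on or before the DCO with an entirely missing date as an OS event at the last known alive date plus one day. This is the floor within the partial-date rule ("the date of death is imputed as the latest of the last date known to be alive +1" and the date built from the known month or year), so it extends an existing convention.
2. Keep the present censoring rule as a sensitivity analysis, and report the number of patients affected so that OS events and deaths reconcile.
3. State what is done with an undated death that cannot be placed on or before the DCO. Survival calls are made after the DCO and later deaths are censored there, so counting every undated death could turn a post-DCO death into an event.
4. State the matching rule for PFS and DoR when an undated death occurs without earlier progression.

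The cost is a few SAP sentences and one extra sensitivity run, with no new data. The imputed time is slightly early, so OS becomes slightly conservative: in the illustrations with a 12-month median, by no more than 0.6 points at 12 months. The change should be made before database lock, so that the choice is not made after the affected patients are known.

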5.2.6.4 Primary Analysis of Secondary Endpoint: OS

The analysis of OS is based on the ITT analysis set. The number and percentage of patients experiencing an OS event and Kaplan-Meier plots of OS will be presented. The median OS and two-sided 95% CI will be estimated using the Kaplan-Meier method (if patient numbers allow).

Summaries of the number and percentage of patients who have died, those still in survival follow-up, those lost to follow-up and those who have withdrawn consent will be provided.

A summary of the ‘potential’ duration of follow-up for OS is included using median (range). This is presented separately for censored patients.

The proportion of patients alive at every 3 months (3, 6, 9, 12, etc.) and associated two-sided 95% CI will be estimated using the Kaplan-Meier method.

5.2.6.5 Sensitivity Analysis of OS Endpoint

A sensitivity analysis will also be conducted to assess the impact of COVID-19 related deaths on OS. That is, patients who had a OS event due to death where the primary or secondary cause of death was COVID-19 infection or COVID-19 infection was reported as a fatal AE, will be censored on the date of their COVID-19 infection related death.

5.3 Pharmacodynamic Endpoint(s)

Refer to the individual modules.

5.4 Pharmacokinetics

For the definitions of the pharmacokinetic variables refer to the individual modules.

AZD0466 exposure is evaluated indirectly by AZD4320 concentration measurement. The term ‘total’ AZD4320 is defined as the sum of dendrimer-conjugated AZD4320 and released AZD4320. ‘Released’ AZD4320 in the plasma is the sum of protein bound and unbound AZD4320, which is not dendrimer-conjugated.

5.4.1 Pharmacokinetic Concentrations

Plasma concentrations of total and released AZD4320 and its metabolites (if available and appropriate) will be listed by actual and relative (to dose administration) sampling time. The following summary statistics will be presented for the concentrations at each time point separately by dose level and dose level/cohort:

- n below LLOQ (only for concentrations)
- Geometric Mean (gmean, calculated as $\exp[\mu]$, where μ is the mean of the data on a logarithmic scale)
- Geometric CV% (gCV, calculated as $100 \sqrt{[\exp(s^2)-1]}$, where s is the standard deviation of the data on a log scale)
- Gmean + gSD (gSD calculated as $\exp[\mu \pm s]$)
- Gmean - gSD
- Arithmetic Mean
- Arithmetic SD (SD)
- Minimum
- Median
- Maximum
- Number of observations

In listings, concentrations below the lower limit of quantification (LLOQ) will be presented as BLQ. In listings and tables where the terms BLQ or LLOQ are included, the LLOQ (numerical value) will be included in a footnote.

For the calculation of statistics, concentrations that are BLQ will be handled as follows at each time point:

- If $\leq 50\%$ of the concentrations are BLQ, all BLQ values will be set to the LLOQ, and all descriptive statistics will be calculated.
- If $>50\%$, but not all, of the concentrations are BLQ, the geometric mean, geometric CV, arithmetic mean, and arithmetic SD will be reported as 'NC' (not calculable). The maximum value will be reported from the individual data, and the minimum and median will be set as 'BLQ'.
- If all concentrations are BLQ, no descriptive statistics will be calculated. 'NA' (not applicable) will be presented for geometric CV, and arithmetic SD, and 'BLQ' will be presented for geometric mean, arithmetic mean, median, minimum, and maximum.

For PK concentration and parameter data, if there are <3 values available at a time point, only the maximum, minimum, and n will be reported; the remaining descriptive statistics will be reported as 'NC'. Concentrations that are BLQ are considered a value.

Missing samples will be reported as no sample ("NS") and excluded from analysis.

Source data shall be used in all derived PK concentrations without prior rounding

The following figures, in black and white, will be generated for total and released AZD4320, and its metabolites (if available and appropriate):

- Patient Profiles, Plasma Concentration Time Data – Linear Scale
- Patient Profiles, Plasma Concentration Time Data - Semi-Logarithmic Scale
- Gmean (\pm gSD), Plasma Concentration Time Data
- Gmean, Plasma Concentration Time Data - Semi-Logarithmic Scale

Individual figures will be plotted using concentration versus actual time, and mean figures will be plotted using concentration versus nominal time, by treatment or dose level and cycle/PK day, as needed. Scatter plots of PK parameters versus dose, or log-dose, may also be considered to assess dose proportionality.

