λz lower	Lower (earlier) t used for λz determination
λz upper	Upper (later) t used for λz determination
λzN	Number of data points used for λz determination
Rsq	Statistical measure of fit for the regression used for λz determination
Rsq adj	Statistical measure of fit for the regression used for λz determination adjusted for the number of used data points (n obs)

Additional PK parameters may be calculated as appropriate.

Pharmacokinetic Summary Statistics

Plasma concentrations of AZD4320 will be summarised by nominal sample time. Plasma concentrations and derived PK parameters will be summarised by dose level and cohort. Plasma concentrations at each timepoint will be summarised according to dose and cohort by the following summary statistics:

- The geometric mean (g_{mean} , calculated as $\exp[\mu]$, where μ is the mean of the data on a logarithmic scale)
- Coefficient of variation (calculated as $100 \sqrt{[\exp(s^2)-1]}$, where s is the standard deviation of the data on a log scale)
- $G_{\text{mean}} \pm$ standard deviation (calculated as $\exp[\mu \pm s]$)
- Arithmetic mean calculated using untransformed data

- Standard Deviation calculated using untransformed data
- Minimum
- Maximum
- Number of observations

The following summary statistics will be presented for the estimated PK parameters, as appropriate:

- G_{mean} , calculated as $\exp[\mu]$, where μ is the mean of the data on a logarithmic scale)
- Coefficient of variation (calculated as $100 \sqrt{[\exp(s^2)-1]}$, where s is the standard deviation of the data on a log scale)
- Arithmetic mean calculated using untransformed data
- Standard deviation calculated using untransformed data
- Minimum
- Maximum
- Number of observations

The PK data for AZD4320 will also be displayed graphically. Displays will include AZD4320 (total and released) plasma concentration patient profiles (on the linear and log scale) versus time and G_{mean} concentration (\pm standard deviation) versus time, stratified by dose.

Scatter plots of PK parameters versus dose, or log-dose, may also be considered to assess dose proportionality.

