3 CHANGES TO PROTOCOL PLANNED ANALYSES - CORE

Not Applicable.

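### SAP 5.4.1 and 5.4.2 give the formula for the PK limits, exp[μ ± s], as the formula for the geometric SD; applied literally, the limits and error bars would be wrong

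*SAP*

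**What the plan says.** SAP 5.4.1 defines the geometric mean as exp[μ], "where μ is the mean of the data on a logarithmic scale", and the geometric CV as 100√(exp(s²) − 1), "where s is the standard deviation of the data on a log scale". Both are standard. The next line is "Gmean + gSD (gSD calculated as" exp[μ ± s]). The line after it is Gmean − gSD, with no formula of its own. SAP 5.4.2 repeats both lines for the derived PK parameters. The figure list in 5.4.1 includes a mean concentration-time plot of Gmean with ± gSD and, separately, a semi-logarithmic mean plot of Gmean alone.

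Protocol 9.4.4 also plans Gmean ± SD for the concentrations at each timepoint, but it attaches the formula to the whole expression: Gmean ± "standard deviation (calculated as" exp[μ ± s]). Its list of statistics for the PK parameters has no such line.

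SAP Section 3, on core changes from the protocol's planned analyses, reads "Not Applicable", and SAP Section 9 says the same for Module 1.

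**The concern.** The two documents use one formula for two different quantities. In the protocol, exp[μ ± s] is the limits. In the SAP, the parenthesis makes it the gSD, which is then to be added to and subtracted from Gmean. That cannot be right. A geometric SD is a single dimensionless factor, exp(s), whereas exp[μ ± s] is two values in concentration units. Adding it to exp[μ] brings the mean in twice.

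At stake are the upper and lower descriptive limits in the PK concentration and parameter tables and the error bars of one figure type. PK is a secondary objective for Parts A and B, so these outputs will be reported. SAP 4.3.1 provides for independent checking of outputs, but a checker who works from the same sentence could repeat the same error.

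**Working it through.** **Inputs.** From SAP 5.4.1: Gmean = exp(μ), s = SD of the log data, gCV = 100√(exp(s²) − 1). The documents contain no PK values, so Gmean = 100 and the values of s (or gCV) are assumptions for illustration. There is no stated figure to reproduce.

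**Correct limits (protocol 9.4.4).** Lower = exp(μ − s) = Gmean / exp(s). Upper = exp(μ + s) = Gmean × exp(s).

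**SAP taken literally, signs matched.** Lower = exp(μ) − exp(μ − s) = Gmean × (1 − exp(−s)). Upper = exp(μ) + exp(μ + s) = Gmean × (1 + exp(s)).

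**Numbers for s = 0.5** (gCV = 100√(exp(0.25) − 1) = 53.3%), with exp(0.5) = 1.6487 and exp(−0.5) = 0.6065:

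- Correct: 100 × 0.6065 = 60.7 and 100 × 1.6487 = 164.9.
- Literal: 100 − 60.65 = 39.3 and 100 + 164.87 = 264.9.

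**Across a range of variability**, with s = √(ln(1 + (gCV/100)²)) and Gmean = 100:

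| gCV | s | Correct limits | Literal, signs matched |
|---|---|---|---|
| 10% | 0.100 | 90.5 to 110.5 | 9.5 to 210.5 |
| 30% | 0.294 | 74.6 to 134.1 | 25.4 to 234.1 |
| 50% | 0.472 | 62.4 to 160.4 | 37.6 to 260.4 |
| 100% | 0.833 | 43.5 to 229.9 | 56.5 to 329.9 |
| 150% | 1.086 | 33.8 to 296.1 | 66.2 to 396.1 |

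Two features show that the literal reading is not a usable summary. The upper limit is always too high by exactly one Gmean. The lower limit moves towards the mean as variability grows, which is the wrong direction; it agrees with the correct value only where 1 − exp(−s) = exp(−s), that is at s = ln 2 ≈ 0.69.

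**The case against.** The strongest reply is that this is a misplaced parenthesis and nobody would program it literally. One SD cannot have two values, so the ± inside the formula shows that it was meant to cover the two adjacent lines, with Gmean + gSD and Gmean − gSD serving as labels for exp(μ + s) and exp(μ − s). The second line has no formula because the first supplies both. SAP Section 1 says the SAP is to be read together with the protocol, the protocol has the formula right, and no departure is declared. The same tables also carry a correct geometric CV, which would visibly disagree with misprogrammed limits. Most of this stands. A slip is the likeliest explanation, and a programmer who treats the bracketed expression as the limits gets correct output. The table and figure specifications are in a separate document that could not be checked.

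Two things remain. The SAP sentence itself is wrong in both sections. And the protocol covers only concentrations: for PK parameters the statistic exists only in the SAP, so there is no protocol formula to fall back on.

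A reader might also infer stronger consequences, which the documents do not support:

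- *Negative lower limits.* These arise only if exp(μ + s) is subtracted on the Gmean − gSD line (100 − 164.9 = −64.9 in the example). With signs matched, the lower value is Gmean × (1 − exp(−s)), which cannot be negative.
- *Error bars that cannot be drawn on a log axis.* The semi-logarithmic mean figure lists Gmean without error bars, and no log scale is stated for the Gmean (± gSD) figure.
- *A distorted assessment of dose proportionality.* Both documents assign that to optional scatter plots of PK parameters against dose or log-dose, and do not call for these limits there.

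**Conclusion.** The point holds as a misstated formula in SAP 5.4.1 and 5.4.2. The expression labelled gSD is the pair of limits, and using it as an additive SD gives wrong limits: 39.3 to 264.9 in place of 60.7 to 164.9 for an assumed Gmean of 100 and s = 0.5. The algebra does not depend on those assumptions; the size of the discrepancy does.

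The importance is minor. The effect is confined to descriptive limits in the PK tables and to the error bars of the Gmean (± gSD) figure, and it occurs only if the SAP is programmed literally. Gmean and geometric CV have correct formulas of their own. Dose escalation and the MTD rest on DLT rates, and no efficacy endpoint uses these statistics.

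**What to change.** In SAP 5.4.1 and 5.4.2:

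- Define gSD = exp(s).
- Replace the two additive lines with Gmean × gSD = exp(μ + s) and Gmean / gSD = exp(μ − s).
- State that the error bars in the Gmean (± gSD) figure are these same limits.

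The labels must change along with the definition. Setting gSD = exp(s) but still adding and subtracting would give 100 ± 1.65, or 98.4 to 101.6, in the example, which is also wrong.

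For concentrations this restores the protocol formula. For PK parameters it corrects a statistic that only the SAP adds. The cost is four lines of SAP text, two in each section, plus a note on the figure, and a check that the separate output specifications agree. No data, design or analysis-set change is needed.
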